### **DESIGN AND PROCEDURES**

We propose to obtain consent from a total of 400 participants in order to identify 120 who meet all inclusion and exclusion criteria and complete all aspects of the study. During a phone screening interview, the study will be described in detail and preliminary participant characteristics (e.g. age, number of cigarettes per day) will be assessed. Participants will be made aware of all exclusion criteria. Those participants who meet criteria for participation will be invited to our offices for an informed consent and screening visit.

**Screening session.** During screening, all aspects of the study will be described to subjects and informed consent will be acquired. Breath and saliva samples will be collected in order to verify smoking status and blood alcohol level (BAL); and measures including, but not limited to, smoking history, nicotine dependence, and mood will be collected. Vitals such as heart rate, blood pressure and weight/height will also be measured. Urine samples will be obtained in order to screen for illicit drug use. Use of illegal drugs will be exclusion criteria, except for marijuana. A blood sample will be obtained in order to assess pregnancy status and blood chemistry as part of the medical evaluation. The medical evaluation will be conducted by the study physician and will include medical history, physical exam, and electrocardiogram (ECG). Participants will also be interviewed regarding their smoking behavior including an assessment of contexts (places) in which they smoke and abstain from smoking cigarettes. At the end of the screening session, if participants qualify to continue in the study (excluding review of lab work) they will complete 2 computer tasks where they will look at pictures of tobacco retail outlets and cigarette point of sale displays. During the tobacco retail outlet task subjects will indicate whether the retail location being shown is personally familiar to them. During the point of sale task subjects will indicate whether they would purchase an item in the display. During each task we will collect eye tracking data using an eyetracker.

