**Randomization and Medication.** Smokers will be randomized (stratified according to gender and smoking frequency) to one of three study drug combinations : placebo patch and capsule (PLAC; n=40), transdermal nicotine patch/placebo capsule (NRT; n=40) or varenicline/placebo patch (VAR; n=40) in a double blind, double-dummy design. The ratio of participants assigned to each group will be 1:1:1. Once participants have been randomized they will receive an 8 day supply of study drugs and instructions for use. Participants will undergo a 7 day induction phase where those in the VAR group and NRT group will be titrated up to a full dose of study drug (see description below) and then all participants will continue on their study drug for 7 more days while they complete two cue reactivity sessions. Following completion of the cue reactivity sessions, all participants will make a quit attempt. Participants in the VAR and NRT groups will continue to receive study drug as usual for the remaining 10 weeks of the study. Participants in the PLAC group will switch to wearing a nicotine patch (21mg if  $\geq 10$  cigarettes/day, 14mg if  $< 10$  cigarettes/day) the morning of their quit day in order to provide them with the minimum standard of care. Figure 1 describes the study drug schedule for dispensing patches and capsules. Participants will be given an extra 3 day supply of capsules and patches at each visit.

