**Cue-Reactivity sessions.** In the week following the study drug induction phase there will be 2 cue-reactivity sessions, which will be at least 24 hours apart but less than 72 hours apart. The first cue-reactivity session will take place 8 days (+ 2 day window) after the randomization visit. Both 1 hour cue-reactivity sessions will begin following 6 hours smoking abstinence. Participants will provide breath and saliva samples. To verify smoking abstinence, the breath CO level must be less than 60% of the highest CO measurement obtained from either the screening session or training session. Subjective and behavioral responses will be assessed in two separate laboratory sessions—one involving reactivity to personal smoking environment cues; the other reactivity to personal nonsmoking environment cues (order randomly assigned and counterbalanced). Following CO assessment, participants will be seated in front of a computer monitor. Participants will be video recorded using a handheld recorder during the session to gather data about their smoking behavior. They will be instructed that throughout the session pictures of places will appear on the screen and they are to focus intently on the environment they see in front of them. The cue-reactivity (CR) sessions will be computer automated: participants will 1) complete on-screen assessments of craving and mood 2) view personal smoking or nonsmoking environment cues, and 3) complete assessments a 2nd time. Following completion of the 2nd assessment, participants will be instructed to watch the slides and concentrate on their content, followed immediately by a screen stating that “At any time from this point on, you may smoke as much as you like until the end of the session. You do not have to smoke if you choose not to.” The environment cues will then be presented for the next 12 minutes. During this ad lib smoking period, choice to smoke, latency to first puff and other smoking topography will be collected while the participant focuses on the picture cues. Following the ad lib period, a prompt to complete assessments will again appear. During the task, heart rate and respiration will be measured using a BIOPAC system.

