## **DATA ANALYSIS**

Reactivity variables (craving, latency to smoke, and smoke intake) will be entered into 3 (Study drug: NRT, VAR, PLAC) x 2 (Environment: smoking, nonsmoking) x 2(Time) repeated measures ANOVAs with random-effects. We hypothesize that personal smoking, as compared to nonsmoking environments, will be associated with greater reactivity (i.e. increased craving and smoke intake; decreased latency to smoke). A Medication x Environment X Time interaction will be characterized by decreased reactivity to smoking as compared to nonsmoking environments in the VAR and NRT groups as compared to the PLAC group.

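### For craving, the planned three-way interaction is a valid change-score test; adjusting for the pre-cue smoking-minus-nonsmoking difference would usually be more precise, by an amount the documents do not fix

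*Combined protocol and SAP*

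**What the plan says.** The DATA ANALYSIS section puts craving, latency to smoke and smoke intake into one model form: study drug at three levels, "x 2 (Environment: smoking, nonsmoking) x 2(Time) repeated measures ANOVAs with random-effects". It names no covariate. The drug hypothesis is stated as an interaction: "A Medication x Environment X Time interaction will be characterized by decreased reactivity to smoking as compared to nonsmoking environments" in the two active arms compared with placebo.

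The Cue-Reactivity sessions paragraph describes two sessions per participant, one per cue type, with the order "order randomly assigned and counterbalanced". In each session participants "complete on-screen assessments of craving and mood 2) view personal smoking or nonsmoking environment cues, and 3) complete assessments a 2nd time". An ad lib smoking period comes next, and then a third round: "Following the ad lib period, a prompt to complete assessments will again appear". The analysis section does not say which two of these three assessments make up Time.

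On timing, "The first cue-reactivity session will take place 8 days (+ 2 day window) after the randomization visit", so every craving score in these sessions is taken on study drug. On size, the plan aims to "identify 120 who meet all inclusion and exclusion criteria and complete all aspects of the study", in three equal arms, for example "placebo patch and capsule (PLAC; n=40". No alpha, power, effect size, SD or correlation is given.

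**The concern.** Entering the pre-cue score as a level of Time subtracts it from the post-cue score one for one. Craving differences between two sessions on different days are noisy. If the pre-cue difference only partly predicts the post-cue difference, subtracting all of it adds noise. Estimating the coefficient from the data avoids that. At stake is precision on the craving test of the drug hypothesis, with 40 participants per arm and no documented power, when the covariate is already being collected.

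**Working it through.** **Inputs.** From the documents: 120 completers, 40 per arm, 1:1:1; craving before and after cues in both sessions; randomised session order. Assumed, because not given: the correlation r between P and D, the SD ratio λ = SD(D)/SD(P), and a two-sided 5% test. The plan has no figure of its own to reproduce.

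**Step 1: what the interaction tests.** For each participant let D = post-cue craving (smoking session) − post-cue craving (nonsmoking session), and let P be the same difference before the cues. With complete data and Time read as pre-cue/post-cue, the interaction estimate is the arm difference in the mean of (post − pre) in the smoking session minus (post − pre) in the nonsmoking session, which equals D − P.

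**Step 2: relative variance.** With SD(P) = 1:
- change score: Var(D − P) = λ² + 1 − 2rλ
- D adjusted for P: λ²(1 − r²)
- ratio = λ²(1 − r²) / (λ² + 1 − 2rλ), which becomes (1 + r)/2 when λ = 1

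The ratio is 1 (no gain) when the slope rλ = 1; otherwise it is below 1.

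**Step 3: numbers.**

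| λ | r = 0.3 | r = 0.5 | r = 0.7 |
|---|---|---|---|
| 0.8 | 50% less | 43% less | 37% less |
| 1.0 | 35% less | 25% less | 15% less |
| 1.2 | 24% less | 13% less | 3% less |

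Example, λ = 1.2 and r = 0.5: 1.44 × 0.75 / (1.44 + 1 − 1.20) = 1.08/1.24 = 0.871. At r = 0.7 and λ = 1.4 the slope is 0.98 and the ratio is 0.9996/1.00, so there is essentially no gain.

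Estimating the slope of P at N = 120 costs a factor of about 1 + 1/115. At λ = 1 the cuts become 34.4%, 24.3% and 14.3%.

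**Step 4: which r is relevant.** It is the correlation between differences, not between raw scores. If all across-session correlations are equal, r = (ρ within − ρ across)/(1 − ρ across). For example, 0.8 within and 0.6 across gives 0.2/0.4 = 0.5. Taking 0.6 to 0.9 within and 0.3 to 0.7 across gives r from 0 to 0.86, hence cuts of 50% down to 7% at λ = 1. Allowing λ above 1 brings the lower end to about 0.

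**Step 5: what this means for power.** Take one drug-versus-placebo contrast with 80% power under the change score. Adjusted power = Φ(2.80/√ratio − 1.96):
- λ = 1: 93.5%, 90% and 86% at r = 0.3, 0.5 and 0.7. Equivalent sample sizes are 40/0.65 ≈ 62, 40/0.75 ≈ 53 and 40/0.85 ≈ 47 per arm.
- λ = 1.2: ratios 0.762, 0.871 and 0.966 give 89%, 85% and 81%.

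**Step 6: is the target the same?** Simulation used 4,000 trials per setting, 40 per arm, a true effect of −0.50 and a drug that lowers craving by 0.8 SD in both sessions:
- Change score and D adjusted for P both averaged −0.50, with variance cuts of 33%, 27% and 15% at r = 0.3, 0.5 and 0.7.
- Adjusting for the smoking session's pre-cue score alone gave −0.41, −0.34 and −0.28.
- Adjusting for the average pre-cue level raised variance by 8% at r = 0.5 and 85% at r = 0.7. When reactivity depended on that level, it also moved the estimate (−0.50 against −0.66 for the change score).
- A drug-specific shift of 0.2 SD in the pre-cue difference separated the two analyses: −0.44 with P as covariate, −0.54 for the change score. Neither returned the −0.50 built in.

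**The case against.** The strongest objection is that pre-cue craving is not a baseline. It is measured more than a week into treatment, and conditioning on a post-randomisation variable can distort a treatment comparison. That is decisive against adjusting for one session's score or for the average level. It is not decisive against P: a background drug effect common to both sessions cancels in the difference, no cue has been shown at the first assessment of that session, and order is randomised. What is needed is that the expected P is equal across arms, not that it is exactly zero.

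Part of the objection stands. Participants photograph their own places and review the pictures with staff, and there is one session per cue type. After the first session they can guess what the second will show. A drug that dampens environment reactivity might also dampen anticipation, and drug-specific carryover would act in the same way. Either would make the two analyses disagree.

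It is also fair to say that a slope of 1 is natural for this design: if the cues simply add a response unrelated to P, the change score is already efficient. Varied responses to cues push λ above 1 and shrink the gain.

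A reader might infer four stronger claims, none of which the documents support:
- That the planned test is biased or invalid. It is neither.
- That 15 to 35% of variance is lost regardless. That range needs r between 0.3 and 0.7 and equal SDs, and the documents give neither.
- That only perfect correlation spares the change score. The condition is rλ = 1, which can hold with r below 1.
- That all three reactivity variables gain. Latency and smoke intake come from the ad lib period and have no pre-cue value.

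**Conclusion.** The point holds for craving, with Time read as pre-cue versus post-cue. The planned interaction is a valid change-score test, and adjusting D for P aims at the same target and is at least as precise in large samples. If the slope happens to be 1, the loss from estimating it is about 1% at N = 120. The gain cannot be pinned down from the documents. It is 15 to 35% of variance under the assumed correlations and equal SDs, 3 to 24% if the post-cue SD is 1.2 times the pre-cue SD, and plausibly anywhere from about 0 to 50%. The unchanged target rests on there being no drug-specific carryover or anticipation in the pre-cue difference. This is a worthwhile efficiency improvement, not a correction of an error.

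**What to change.** For craving, amend the DATA ANALYSIS section as follows:
- State which assessments are used. Take the second one (after the cues, before ad lib smoking) as the outcome.
- Compare arms on D, with P as covariate, plus session order and the two randomisation strata (gender and smoking frequency).
- Do not use one session's pre-cue score, or the average pre-cue level alone, as the covariate. If a mixed model is fitted, split pre-cue craving into the person mean and the within-person deviation, so that a background drug effect does not enter the environment contrast.
- Keep the 3 × 2 × 2 change-score analysis as a sensitivity analysis, and report mean P by arm and session order. Disagreement between the two analyses would point to carryover or anticipation.

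The cost is analysis wording and a few degrees of freedom: one each for P, session order and gender, and at least one for smoking frequency, so 117 residual degrees of freedom become at most 113. No new data are needed. The models for latency and smoke intake are unaffected by this point.

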## **RISK/BENEFIT ASSESSMENT**

Blood drawing: Momentary discomfort and/or bruising can occur; infection, excess bleeding, clotting or fainting are possible although unlikely.

Needle stick: There will be mild, momentary pain associated with the needle stick for the needle placement. There is a minimal risk of bruising, bleeding and mild discomfort associated with the needle stick. A small risk of infection at the site of the needle stick can also occur. The use of clean techniques should keep this risk low.

Concomitant smoking and NRT. The currently approved package insert for Nicoderm CQ no longer warns against concurrent use of the patches and cigarette smoking. Thus, we do not believe there are additional health risks associated with the concurrent use of these products above smoking cigarettes alone.

Nicotine Patch. Insomnia and abnormal dreams are common and expected side effects associated with

24 hour nicotine patches. If a subject complains of disturbed sleep, he or she will be instructed to remove the patch at bedtime and apply a new one the next day at the usual time. Skin irritation may occur, although this will be minimized by changing the site of patch application daily. Using 1% hydrocortisone cream on the affected area will be recommended to help reduce skin irritation. If a subject develops itching or a rash at the patch site, he or she will be advised to use 1% hydrocortisone cream on the affected area. Symptoms associated with nicotine toxicity include, lightheadedness, dizziness, nausea, fainting and vomiting. Symptoms considered moderate to severe in nature will be evaluated by the study medical staff by telephone or in person, depending upon the level of severity. Upon evaluation, the subject will then be given the choice of continuing in the study while discontinuing patch use.

Varenicline. The main side effects accompanying use of varenicline (Chantix®) are nausea, vomiting, gas, insomnia, and vivid dreams. If troublesome symptoms occur, the dose may be reduced to 1 mg daily (discontinuing the second dose) or discontinued altogether. Rarely, more serious side effects can occur including changes in behavior, hostility, agitation, depressed mood, suicidal thoughts and behavior, and attempted suicide. Participants will be asked about these symptoms at each visit and the study physician will be called in to evaluate the participant if any are endorsed. Until patients know how Chantix affects their ability to tolerate alcohol, they should decrease the amount of alcohol they drink. Patients who have a seizure while taking Chantix should stop the medicine and seek medical attention immediately. At randomization, participants will be given the “Medication Guide” that accompanies prescription Chantix. This information will be reviewed with the participant by study staff and participants will be encouraged to contact study staff upon experiencing any changes in behavior. As is standard in our protocols, all participants will have access to the PI’s cell phone number and the study physician’s pager number.

Women of childbearing potential: Pregnant or nursing women will be excluded from the study. Female participants will undergo a serum pregnancy test at screening. Subjects must also agree to use appropriate contraception during the course of the trial. They will be encouraged in the consent form to notify study staff if they believe a change in their pregnancy status has occurred during the trial.

Management of side effects: Reports of side effects will be obtained by study staff and communicated to the principle investigator and study physician, who will determine the most appropriate course of action, which may include options for termination of study participation. Participants will be reminded of their option to withdraw from the study at any time. If a participant decides to withdraw from the study, we will ask them to return for a final visit to return all study materials. Because all subjects will receive either placebo patches or placebo tablets/capsules, in the event of significant side effects it will be necessary to reduce both patch and oral dosing concomitantly in order to preserve the double blind while ensuring a dose reduction in the active treatment. In response to complaints of insomnia, instructions will be given to remove skin patches at bedtime and discontinue the second daily dose of oral medication. In the event of other intolerable side effects, both patch and oral medications will be discontinued completely

## **PARTICIPANT RECRUITMENT AND COMPENSATION**

We will advertise in local newspapers, the radio, flyers on bulletin boards and on the internet (including but not limited to trianglesmokingstudies.com and craigslist). When we receive calls from potential subjects we will return their call and ask information including name, address, age, and smoking history. Potential subjects may also complete an on-line Qualtrics screening survey accessed from our website. They will be given a brief description of our studies and will be asked questions to determine interest and eligibility. If they do qualify we will schedule a screening session where we will follow all IRB protocols of informed consent.

Participants will receive \$10 at the screening session if they pass the drug test, breath alcohol test and CO test. Individuals who do not pass these tests will be dismissed from the screening visit without payment, except in the event they can produce a current, valid prescription for the medication that caused them to fail the drug test. Participants will also receive \$25 for completing the training session, \$25 for the camera return/randomization visit plus \$25 in cash if they returned complete and useable photos within one week of the training session, \$50 for each cue-reactivity session (\$100 total), \$30 for each post-quit lab visit (\$120 total) and a \$100 at the end of the study if they complete all sessions (up to \$405 total). Participants may also earn \$2 each day they complete the Qualtrics surveys on time (up to \$196) and \$10 for completing a 6 month post quit date follow-up phone call. Participants will also earn up to \$10 for wearing the Metria device if they choose to participate in this part of the study. Participants that decide to withdraw from the study before fulfilling all of the requested tasks will be given compensation for each session completed.

## **DATA AND SAFETY MONITORING**

The Principal Investigator will report all serious adverse events and unanticipated findings and problems relating to the study in an expedited manner to the Duke University Health System (DUHS) Institutional Review Board (IRB) office and all applicable regulatory authorities in accordance with standard operating procedures.

## **COSTS TO PARTICIPANTS**

There are no costs to participants for taking part in this study. All the study costs, including any procedures related directly to the study, will be paid for by the study.

## **DATA STORAGE AND CONFIDENTIALITY**

Participants will be informed, in their consent forms, of the data storage and confidentiality safeguards, which are practiced according to current HIPAA regulations.

Except when required by law, the participant will not be identified by name, social security number, address, telephone number or any other direct personal identifiers in the study records.

All photographic images acquired by participants will be reviewable by participants prior to upload to the secure server. Data from the server can only be accessed by authorized study staff with a username and password. All photographs of private locations taken by participants will be destroyed by the PI or CRC upon completion of the study. Photographs that include persons not known to subject will be deleted. The participant will be assigned a unique code number and the key to the code will be kept in a locked room accessible to the study coordinator.

Blood samples coded with participant number, initials and birth year will be sent to LabCorp, [name] for blood chemistry and serum pregnancy testing. LabCorp work order #37 outlines the agreement for this protocol.

[name] at UPMC will be a collaborator for the study. She is listed as outside key personnel and will not have access to any study PHI or identifiable information.
